
Potassium <math>\geq</math> 6.0 mmol/L (6.0 mEq/L) and/or symptomatic (e.g., muscle cramps, weakness, paresthesias, nausea, vomiting, diarrhea)
	
 
• Perform STAT ECG and commence telemetry
 
• Nephrology assessment with consideration of initiating dialysis
 
• Administer Kayexalate 60g
 
• Administer furosemide 20mg IV x1
 
• Administer insulin 0.1 U/kg IV + D25 2 mL/kg IV
 
• Administer sodium bicarbonate 1 to 2 mEq/kg IV push
 
• If sodium bicarbonate is used, rasburicase should not be used as this may exacerbate calcium phosphate precipitation
 
• Administer calcium gluconate 100 to 200 mg/kg IV slowly if there is ECG/telemetry evidence of life-threatening arrhythmias. Do not administer in same IV line as sodium bicarbonate.
 
• Recheck potassium, phosphorous, uric acid, calcium and creatinine every hour STAT
 

Hyperuricemia
 
Uric acid <math>\geq</math> 8 mg/dL (476 <math>\mu</math>mol/L)
	
 
• Consider rasburicase (dose based on institutional standards)
 
• If rasburicase is used, sodium bicarbonate should not be used as this may exacerbate calcium phosphate precipitation
 
• Recheck potassium, phosphorous, uric acid, calcium, and creatinine in 1 hour STAT.
 

[figure not shown]

Uric acid <math>\geq</math> 10mg/dL (595 <math>\mu</math>mol/L) OR Uric acid <math>\geq</math> 8 mg/dL (476 <math>\mu</math>mol/L) with 25% increase and creatinine increase <math>\geq</math> 0.3 mg/dL (<math>\geq</math>0.027 mmol/L) from predose level
	
 
• Administer rasburicase (dose based on institutional standard)
 
• If rasburicase is used, sodium bicarbonate should not be used as this may exacerbate calcium phosphate precipitation
 
• Notify nephrology
 
• Recheck potassium, phosphorous, uric acid, calcium, and creatinine in 1 hour STAT.
 
• If uric acid <math><</math> 8.0 mg/dL 1 hour later, repeat potassium, phosphorous, uric acid, calcium, and creatinine 2 and 4 hours, later, if no other evidence of tumor lysis
 

Hypocalcemia	

Calcium <math>\leq</math> 7.0 mg/dL (1.75 mmol/L) AND subject symptomatic (e.g., muscle cramps, hypotension, tetany, cardiac arrhythmias)
	
 
• Administer calcium gluconate 50 to 100 mg/kg IV slowly with ECG monitoring
 
• Telemetry
 
• Recheck potassium, phosphorous, uric acid, calcium, and creatinine in 1 hour STAT.
 
• If calcium normalized 1 hour later, repeat potassium, phosphorous, uric acid, calcium and creatinine 2 and 4 hours, later if no other evidence of tumor lysis
 
• Calculate corrected calcium and check ionized calcium if albumin low
 

Hyperphosphatemia	

Phosphorus $\geq$ 5.0 mg/dL (1.615 mmol/L) with $\geq$ 0.5 mg/dL (0.16 mmol/L) increase	
 
Administer a phosphate binder (e.g., aluminum hydroxide, calcium carbonate, sevelamer hydroxide or lanthanum carbonate).
 
Nephrology notification (dialysis required for phosphorus <math>\geq</math> 10mg/dL)
 
Recheck potassium, phosphorous, uric acid, calcium, and creatinine in 1 hour STAT
 
If phosphorous <math><</math> 5.0 mg/dL 1 hour later, repeat potassium, phosphorus, uric acid, calcium, and creatinine 2 and 4 hours, later, if no other evidence of tumor lysis
 

Creatinine	
Increase $\geq$ 25% from baseline	
 
Start or increase rate of IV fluids
 
Recheck potassium, phosphorous, uric acid, calcium, and creatinine in 1 to 2 hours STAT
 

## APPENDIX D PATIENT WALLET CARD

**INSTRUCTIONS FOR PATIENT WALLET CARD TEMPLATE-** Give the wallet card to the patient at the time of enrollment. The patient will cut out the wallet-sized information card and retain it at all times

[figure not shown]
### PATIENT CLINICAL TRIAL WALLET CARD

**APPENDIX E NIVOLUMAB AE MANAGEMENT ALGORITHM: MANAGEMENT ALGORITHMS FOR  
ENDOCRINOPATHY, GASTROINTESTINAL, HEPATIC, NEUROLOGICAL, PULMONARY, RENAL, AND SKIN  
ADVERSE EVENTS**

## Endocrinopathy Management Algorithm

[figure not shown]
Rule out non-inflammatory causes. If non-inflammatory cause, treat accordingly and continue immuno-oncology (I-O) therapy.  
Consider visual field testing, endocrinology consultation, and imaging.

Patients on IV steroids may be switched to an equivalent dose of oral corticosteroids (e.g. prednisone) at start of tapering or earlier, once sustained clinical improvement is observed. Lower bioavailability of oral corticosteroids should be taken into account when switching to the equivalent dose of oral corticosteroids.

## GI Adverse Event Management Algorithm

[figure not shown]
Rule out non-inflammatory causes. If non-inflammatory cause is identified, treat accordingly and continue I-O therapy. Opiates/narcotics may mask symptoms of perforation. Infliximab should not be used in cases of perforation or sepsis.

Patients on IV steroids may be switched to an equivalent dose of oral corticosteroids (e.g. prednisone) at start of tapering or earlier, once sustained clinical improvement is observed. Lower bioavailability of oral corticosteroids should be taken into account when switching to the equivalent dose of oral corticosteroids.

# Hepatic Adverse Event Management Algorithm

Rule out non-inflammatory causes. If non-inflammatory cause, treat accordingly and continue I-O therapy. Consider imaging for obstruction.

[figure not shown]
Patients on IV steroids may be switched to an equivalent dose of oral corticosteroids (e.g. prednisone) at start of tapering or earlier, once sustained clinical improvement is observed. Lower bioavailability of oral corticosteroids should be taken into account when switching to the equivalent dose of oral corticosteroids.

\*I-O therapy may be delayed rather than discontinued if AST/ALT  $\leq 8 \times$  ULN and T.bili  $\leq 5 \times$  ULN.

\*\*The recommended starting dose for grade 4 hepatitis is 2 mg/kg/day methylprednisolone IV.

## Neurological Adverse Event Management Algorithm

[figure not shown]
**Rule out non-inflammatory causes.** If non-inflammatory cause, treat accordingly and continue I-O therapy

Patients on IV steroids may be switched to an equivalent dose of oral corticosteroids (e.g. prednisone) at start of tapering or earlier, once sustained clinical improvement is observed. Lower bioavailability of oral corticosteroids should be taken into account when switching to the equivalent dose of oral corticosteroids.

# Pulmonary Adverse Event Management Algorithm

[figure not shown]
Rule out non-inflammatory causes. If non-inflammatory cause, treat accordingly and continue I-O therapy. Evaluate with imaging and pulmonary consultation.

Patients on IV steroids may be switched to an equivalent dose of oral corticosteroids (e.g. prednisone) at start of tapering or earlier, once sustained clinical improvement is observed. Lower bioavailability of oral corticosteroids should be taken into account when switching to the equivalent dose of oral corticosteroids.

# Renal Adverse Event Management Algorithm

[figure not shown]
Rule out non-inflammatory causes. If non-inflammatory cause, treat accordingly and continue I-O therapy.

Patients on IV steroids may be switched to an equivalent dose of oral corticosteroids (e.g. prednisone) at start of tapering or earlier, once sustained clinical improvement is observed. Lower bioavailability of oral corticosteroids should be taken into account when switching to the equivalent dose of oral corticosteroids.

# Skin Adverse Event Management Algorithm

Rule out non-inflammatory causes. If non-inflammatory cause, treat accordingly and continue I-O therapy.

[figure not shown]

Patients on IV steroids may be switched to an equivalent dose of oral corticosteroids (e.g. prednisone) at start of tapering or earlier, once sustained clinical improvement is observed. Lower bioavailability of oral corticosteroids should be taken into account when switching to the equivalent dose of oral corticosteroids.

\*Refer to NCI CTCAE v4 for term-specific grading criteria.

^If SJS/TEN is suspected, withhold I-O therapy and refer patient for specialized care for assessment and treatment. If SJS or TEN is diagnosed, permanently discontinue I-O therapy.

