### **3.2 Exclusion Criteria**

3.2.1 Patients who have received any prior BCL-2 inhibitor therapy

3.2.2 Patients who have received prior hypomethylating therapy for treatment of AML are excluded

3.2.3 Patients with *known autoimmune disease*. Patients with active autoimmune disease or history of autoimmune disease that might recur, which may affect vital organ function or require immune suppressive treatment including systemic corticosteroids, should be excluded. These include but are not limited to patients with a history of immune related neurologic disease, multiple sclerosis, autoimmune (demyelinating) neuropathy, Guillain-Barre syndrome, myasthenia gravis; systemic autoimmune disease such as SLE, connective tissue diseases, scleroderma, inflammatory bowel disease (IBD), Crohn's, ulcerative colitis, hepatitis; and patients with a history of toxic epidermal necrolysis (TEN), Stevens-Johnson syndrome, or phospholipid syndrome should be excluded because of the risk of recurrence or exacerbation of disease. Patients with vitiligo, endocrine deficiencies including thyroiditis managed with replacement hormones including physiologic corticosteroids are eligible. Patients with rheumatoid arthritis and other arthropathies, Sjögren's syndrome and psoriasis controlled with topical medication and patients with positive serology, such as antinuclear antibodies (ANA), anti-thyroid antibodies should be evaluated for the presence of target organ involvement and potential need for systemic treatment but should otherwise be eligible.

3.2.4 Patients are permitted to enroll if they have vitiligo, type I diabetes mellitus, residual hypothyroidism due to autoimmune condition only requiring hormone replacement, psoriasis not requiring systemic treatment, or conditions not expected to recur in the absence of an external trigger (precipitating event).

3.2.5 Patients should be excluded if they have a condition requiring systemic treatment with either corticosteroids ( $>10$  mg daily prednisone equivalents) or other immunosuppressive medications within 14 days of study drug administration. Inhaled or topical steroids and adrenal replacement doses  $\leq 10$  mg daily prednisone equivalents are permitted in the

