
*Including CHF, LV systolic dysfunction, Myocarditis, CPK, and troponin
 
**Patients with evidence of myositis without myocarditis may be treated according as “other event”
 
Note: The optimal treatment regimen for immune mediated myocarditis has not been established. Since this toxicity has caused patient deaths, an aggressive approach is recommended.
	

All Other Events	Management/Next Dose for Nivolumab
$\leq$ Grade 1	No change in dose.
Grade 2	Hold until $\leq$ Grade 1 OR baseline (exceptions as noted below).
Grade 3	Hold until $\leq$ Grade 1 OR baseline and patient no longer on steroid treatment if initiated (exceptions as noted below). Permanently discontinue for events with a high likelihood of morbidity or mortality with recurrent events.
Grade 4	Off protocol therapy.
Recommended management: As clinically indicated	

- Any Grade 2 drug-related uveitis or eye pain or blurred vision that does not respond to topical therapy and does not improve to Grade 1 severity within the re-treatment period OR requires systemic treatment should go off protocol treatment
- Any Grade 3 or 4 drug-related laboratory abnormality or electrolyte abnormality, that can be managed independently from underlying organ pathology with electrolyte replacement, hormone replacement, insulin or that does not require treatment **does not** require discontinuation.
- Any AE, laboratory abnormality, or intercurrent illness which, in the judgment of the investigator, presents a substantial clinical risk to the subject with continued study drug dosing should go off protocol treatment.

Skin Rash and Oral Lesions	Management/Next Dose for Nivolumab
≤ Grade 1	No change in dose*.
Grade 2	Hold* until 1≤ Grade resolved. Resume at same dose level.
Grade 3	Hold* until ≤ Grade 1. Resume at same level at investigator discretion
Grade 4	Off protocol therapy.

\*Patients with purpuric or bullous lesions must be evaluated for vasculitis, Steven-Johnson syndrome, toxic epidermal necrolysis (TEN), and autoimmune bullous disease including oral lesions of bullous pemphigus/pemphigoid. Pruritus may occur with or without skin rash and should be treated symptomatically if there is no associated liver or GI toxicity. Note skin rash typically occurs early and may be followed by additional events particularly during steroids tapering.

Recommended management: AE management guidelines

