Prior to starting corticosteroids or hormone replacement for any reason, appropriate

endocrine testing including cortisol, Cortrosyn® adrenocorticotropic hormone (ACTH), thyroid stimulating hormone (TSH), and thyroxine (T4) must be obtained to document baseline.

Please note that in some cases the treatment algorithms recommend steroids if symptoms do not resolve in 7 days. However, this recommendation is not meant to delay steroid treatment at any time it is clinically indicated.

Any patient started on corticosteroids initially, who is determined to not require steroid treatment for an autoimmune AE, may resume therapy after a 2-week observation period without further symptoms at the discretion of the PI or investigator.

Any patient requiring high dose steroids (any dose greater than the equivalent to 20 mg prednisone) will be considered to have experienced a DLT and will be taken off nivolumab. These patients will be allowed to continue receiving decitabine and venetoclax on study.

Patients requiring high dose steroid treatment for autoimmune or inflammatory events should go off study treatment except for a short course of tapering steroids for infusion reaction, skin rash or endocrine events.

Patients with grade 3 thyroiditis and skin rash may continue therapy as for grade 2 events with resolution and stable replacement treatment.

Patients with thyroiditis or hypopituitarism who are stable as above may be restarted with replacement hormones including thyroid hormone and physiologic doses of corticosteroids.

Please note that grading and for hypophysitis with symptoms of headache, visual or neurologic changes or radiologic evidence of pituitary enlargement and other CNS events such as aseptic meningitis or encephalitis should be considered grade 3 events.

Patients may be dose-delayed for evaluation and restarted depending on results.

Any patient started on corticosteroids initially who is determined to not require steroid treatment for an autoimmune adverse event may resume therapy after a 2-week observation period without further symptoms at the discretion of the PI or investigator.

If doses of nivolumab are missed/delayed other than reasons for toxicity, they may be given +2 days of scheduled dose.

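### The Section 7.5 skin table and rash sentences for nivolumab do not carry Appendix E's rule for Stevens-Johnson syndrome (SJS) and toxic epidermal necrolysis (TEN), and nothing says which text governs

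*Combined protocol and SAP*

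**What the plan says.** Appendix E, Skin Adverse Event Management Algorithm, has a footnote with two steps. On suspicion: "If SJS/TEN is suspected, withhold I-O therapy and refer patient for specialized care for assessment and treatment". On diagnosis: "If SJS or TEN is diagnosed, permanently discontinue I-O therapy". The footnote attaches no grade to either step.

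Section 7.5 has its own table for skin rash and oral lesions, which sets the next nivolumab dose by grade:

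- Grade 1 or less: dose unchanged.
- Grade 2: nivolumab is held until the event settles, then restarted without a dose change.
- For grade 3 the row reads: "Hold* until ≤ Grade 1. Resume at same level at investigator discretion".
- At grade 4 the patient leaves protocol treatment.

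An asterisk on the first three rows leads to a footnote: "Patients with purpuric or bullous lesions must be evaluated for vasculitis, Steven-Johnson syndrome, toxic epidermal necrolysis (TEN), and autoimmune bullous disease". The footnote does not say what happens to dosing if that evaluation is positive.

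Later text in Section 7.5 lets grade 3 skin rash continue on the grade 2 terms. It also takes patients who need high-dose steroids off study treatment, "except for a short course of tapering steroids for infusion reaction, skin rash or endocrine events". Neither sentence mentions SJS or TEN.

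Section 7.5 opens by sending the reader to the Investigator Brochure or Appendix E. It says the algorithms should be followed unless the treating physician judges another approach clinically appropriate.

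**The concern.** A site deciding on the next nivolumab dose will naturally look at the 7.5 table, because that is the table that sets it. Read alone, the table keeps a patient on an unchanged dose while low-grade lesions are evaluated for SJS/TEN. After a grade 2 or 3 skin event has settled, its rows lead back to dosing, whatever the evaluation found. Appendix E gives a different instruction in both situations.

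What is at stake is consistent handling across sites of a reaction that the nivolumab adverse-event list (Section 10.1.1) places in its rare but serious column, and how much nivolumab an affected patient receives.

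**Working it through.** The plan states no figure here to reproduce. The check is a comparison of the two texts, followed by two small calculations of scale.

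**Step 1: the texts side by side.**

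| Situation | 7.5 skin table | Appendix E footnote | Agree? |
|---|---|---|---|
| Suspected, grade 1 or less | Dose unchanged, evaluation required | Withhold | No |
| Suspected, grade 2 or 3 | Hold, evaluation required | Withhold | Yes, while held |
| Diagnosed, grade 1 or less | Dose unchanged | Permanent stop | No |
| Diagnosed, grade 2 | Hold, then resume | Permanent stop | No |
| Diagnosed, grade 3 | Hold, then resume at discretion | Permanent stop | No |
| Grade 4 | Off protocol therapy | Withhold or permanent stop | Yes: no nivolumab under either |

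In the diagnosed rows the table is silent on SJS/TEN, so its general grade rule applies by default. At grade 3 that default permits resumption but does not require it.

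**Step 2: does other text settle it?** The opening of 7.5 offers the Investigator Brochure or Appendix E, allows departure on physician judgment, and does not rank the appendix against the table. The line under the skin table points to the adverse-event management guidelines, again without ranking. Section 7.1 lets a patient restart after a non-hematologic DLT once the event is at grade 1 or less or back to baseline, with no SJS/TEN exception.

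**Step 3: exposure at issue.** The Schema gives nivolumab on day 15 of cycle 1 and on days 1 and 15 of later cycles. Section 6.3 runs the DLT window from cycle 1 day 15 to the end of cycle 3.

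- Infusions in the window: 1 + 2 + 2 = 5.
- Remaining if the event follows the first: 5 − 1 = 4, so 4/5 = 80%.
- After the window: 2 per cycle.

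This is a ceiling. It assumes no infusion is lost to the holds in the table or Section 7.1, or to the rule in 7.1 that ends study therapy after a delay of more than 6 weeks.

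**Step 4: chance of seeing any case.** The adverse-event list gives only a bound of less than 3% for SJS and TEN, so the rates p below are assumptions. With the maximum of 42 patients (Section 9.2), P(at least one case) = 1 − (1 − p)^42.

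| Assumed p | Calculation | Result |
|---|---|---|
| 0.1% | 1 − 0.999^42 | 0.041 |
| 1% | 1 − 0.99^42 | 0.344 |
| 3% (the bound, itself excluded) | 1 − 0.97^42 | 0.722 |

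These are chances that a case occurs. The chance that the wording matters is smaller: the case must also fall in a grade row where the texts differ, and no other stop rule may apply. For resumption after a diagnosis, the event must also have resolved.

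**The case against.** The strongest reply is that Appendix E is already part of Section 7.5. The section opens by directing the reader there and tells sites to follow it, the skin table ends with a pointer to the management guidelines, and the asterisk ties the SJS/TEN evaluation to the rows themselves. A silent table plus a cross-reference is then a gap in the wording rather than two competing rules. Other text in 7.5 can also stop nivolumab: the steroid rule above 20 mg prednisone equivalent, the substantial-clinical-risk rule, and the permanent-discontinuation wording for grade 3 in the table for all other events.

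Much of this stands, and it narrows the disagreement. It does not close it. The cross-reference allows departure and sets no precedence. The steroid rule depends on dose, and the sentence after it exempts a short taper for skin rash from going off study treatment. The risk rule depends on judgment. The permanent-discontinuation wording sits in a table that skin events do not use.

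Some stronger readings are tempting, but the documents do not support them:

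- That the table asks only for an evaluation. It also holds nivolumab at grades 2 and 3.
- That the table authorizes resumption after confirmed SJS/TEN. It never says so; the result follows only from its silence.
- That the primary safety result changes. Under Section 6.3 a drug-related non-hematologic event of grade 3 or above is a DLT, and the listed exceptions do not cover skin. Such a case counts whichever text is followed, and no change in the DLT count has been shown.
- That exclusion 3.2.3 also needs reconciling. It says patients with a history of SJS or TEN "should be excluded because of the risk of recurrence or exacerbation of disease". It governs entry and conflicts with neither text.

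**Conclusion.** The inconsistency is real and specific. The texts do not agree for suspected SJS/TEN at grade 1 or less or for diagnosed SJS/TEN at grade 3 or less, and no precedence is stated. The size is at most 4 of 5 nivolumab infusions per affected patient in the DLT window. On assumed rates of 0.1% to 1%, the chance of any case among 42 patients is about 4% to 34%, approaching 72% as the rate nears the 3% bound.

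Two limits apply. The Appendix E flow chart is not reproduced in the text available, so only its footnotes could be compared. The documents also do not give the CTCAE grading of SJS or TEN, so they do not show which grades can occur in practice. If low grades never occur, the disagreement shrinks to the grade 3 row. The point should be corrected because it concerns patient safety and costs almost nothing to fix, not because a trial result is shown to depend on it.

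**What to change.** Reconcile the Section 7.5 skin table, the later skin-rash sentences in 7.5 (grade 3 rash continuing as grade 2, and the steroid-taper exemption) and the Appendix E skin footnote, and check the restart rule in Section 7.1 against the result.

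- The sponsor's medical team chooses one rule for suspected and one for diagnosed SJS/TEN. This review does not propose either.
- State that rule in the 7.5 skin table, with its relation to the grade rows made explicit, and repeat it in Appendix E.
- Say in the 7.5 skin-rash sentences whether SJS and TEN are included or excluded.
- Add one sentence to 7.5 saying which text takes precedence where the table and Appendix E differ.

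The cost is a few words in the table, a few sentences in 7.5 and a matching appendix footnote. No extra patients, visits or data are needed.

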# Myocarditis Adverse Event Management Algorithm

Patients on IV steroids may be switched to an equivalent dose of oral corticosteroids (e.g. prednisone) at start of tapering or earlier, once sustained clinical improvement is observed. Lower bioavailability of oral corticosteroids should be taken into account when switching to the equivalent dose of oral corticosteroids.

Prophylactic antibiotics should be considered in the setting of ongoing immunosuppression.

ATG = anti-thymocyte globulin; BNP = B-type natriuretic peptide; ECG = electrocardiogram; IV = intravenous; MRI = magnetic resonance imaging

